## Table 1d. Visit Windows for PGIS

Analysis Visit	Target Analysis Day	Low Analysis Day	High Analysis Day
Week 8	Aday 57	Aday 29	Aday 84
Week 16	Aday 113	Aday 85	Aday 140
Week 24	Aday 169	Aday 141	Aday 196

# Table 1e. Visit Windows for PGIC

Analysis Visit	Target Analysis Day	Low Analysis Day	High Analysis Day
Week 24	Aday 169	Aday 141	Aday 196

# **Table 1f. Visit Windows for Ethmoid Cavity Opacification**

Analysis Visit	Target Analysis Day	Low Analysis Day	High Analysis Day
Week 25/follow-up*	Aenday 7	Aenday 0	Aenday 31

\* post-treatment follow-up.

\* post-treatment follow-up.

# 3.1.2.2 Analysis Visit Windows for Safety Endpoints

# Table 2a. Visit Windows for Laboratory and Slit-Lamp Examination Assessments

Analysis Visit	Target Analysis Day	Low Analysis Day	High Analysis Day
Week 25/follow up*	Aenday 7	Aenday 0	Aenday 31

\* post-treatment follow-up.

## Table 2b. Visit Windows for Nasal Endoscopy Assessments

Analysis Visit	Target Analysis Day	Low Analysis Day	High Analysis Day
Week 4	Aday 29	Aday 2	Aday 56
Week 12	Aday 85	Aday 57	Aday 126
Week 24	Aday 169	Aday 127	Aday 196
Week 25/follow-up*	Aenday 7	Aenday 1	Aenday 31
post-treatment follow-up.			

Table 2c. Visit Windows for IOP Assessments

Analysis Visit	Target Analysis Day	Low Analysis Day	High Analysis Day
Week 4	Aday 29	Aday 2	Aday 56
Week 12	Aday 85	Aday 57	Aday 196
Week 25/follow-up*	Aenday 7	Aenday 0	Aenday 31

\* post-treatment follow-up.

# 3.1.3 Definition of Baseline

For cardinal symptoms (3CS and individual symptoms) and loss of smell score, the baseline is the average of non-missing daily scores over the 7-day period prior to and including Day 1. For other efficacy and safety assessments, the baseline is the last non-missing measurements prior to or on the day of treatment administration.

## 3.1.4 Endpoint Related Definition and Calculation

3.1.4.1 Product-Related Treatment-Emergent Serious Adverse Event (SAE)

Treatment-emergent adverse event is defined in Section 3.6.1.

A product-related treatment-emergent SAE must meet all the following criteria:

- 1. The treatment-emergent adverse event is serious.
- 2. The causality of an SAE is definitely related or possibly related to LYR-220 study drug product according to the investigator's assessment.
- 3.1.4.2 Newly Identified or Worsened Endoscopic Findings (Epistaxis and Mucosal Injury) in Ethmoid Cavity through Week 25/Follow Up

A newly identified endoscopic finding in ethmoid cavity is a development of epistaxis or mucosal injury at post-baseline visits.

A worsened endoscopic finding in ethmoid cavity is an increased severity change of either epistaxis or mucosal injury from baseline.

#### 3.1.4.3 Clinically Significant Increase of IOP through Week 25/Follow Up

A clinically significant increase of IOP is defined as IOP in 1 or both eyes >23 mm Hg or an increase of IOP from Baseline in 1 or both eyes ≥10 mm Hg.

# 3.1.4.4 Newly Identified or Worsened Cataract in 1 or Both Eyes by Slit-Lamp Examination through Week 25/Follow Up

A newly identified cataract is a development of posterior subcapsular cataract of grade 1 or higher, nuclear cataract of grade 1 or higher, or cortical cataract of grade 1 or higher or involving a minimum of center optic zone of 3-mm diameter at post-baseline visits.

A worsened cataract is an increased grade change of posterior subcapsular cataract, nuclear cataract, or cortical cataract from baseline.

#### 3.1.4.5 SNOT-22 through Week 28/Follow Up

The SNOT-22 questionnaire is a 22-item disease-specific quality of life instrument validated for use in CRS. Subjects will score the severity of their symptoms and social/emotional consequences of CRS on a 6-point scale over the past 2 weeks: 0 = no problem, 1 = very mild problem, 2 = mild or slight problem, 3 = moderate problem, 4 = severe problem, and 5 = problem as bad as it can be.

The scores are summed; higher scores on the SNOT-22 instrument total score or subdomain scores (as defined in Table 3) indicate higher severity of symptoms or social/emotional consequences of CRS.

If any of the individual item scores is missing, the total score and the corresponding domain score will be considered missing.

Table 3. Categorized Survey Items for Separate Domains of the SNOT-22 Instrument

SNOT-22 Domains	Survey Items	Score Range
Rhinologic Symptoms	#1, #2, #3, #4, #7, #12	0–30
Extra-Nasal Rhinologic	# 5, # 6, # 7	0–15
Symptoms		
Ear/Facial Symptoms	#3, #8, #9, #10, #11	0–25
Psychological Dysfunction	#16, #17, #18, #19, #20, #21, #22	0–35
Sleep Dysfunction	#13, #14, #15, #16, #17	0–25

#### 3.1.4.6 CRS Cardinal Symptoms through Week 28/Follow Up

Enrolled subjects will be asked to complete a daily ePRO to assess the severity of the 4 CS of CRS (nasal blockage/obstruction/congestion, facial pain/pressure, anterior/posterior nasal discharge, and reduction/loss of smell). Enrolled subjects will start recording their symptoms on the ePRO at least 14 days preceding the Day 1 visit. A minimum of 4 daily entries are required for composite score calculation over the preceding 7 days prior to Day 1 (not including Day 1) for assessing subject's eligibility for participating in the study.

Enrolled subjects will complete the daily assessment of their CS severity each morning (between 06:00:00AM to 11:59:59AM local time) and rate the severity of each symptom at its worst over the past 24 hours on a 4-point scale: 0 = absent symptoms (no sign/symptom evident), 1 = mild symptoms (sign/symptom present but minimal awareness; easily tolerated), 2 = moderate symptoms (definite awareness of sign/symptom that is bothersome but tolerable), and 3 = severe symptoms (sign/symptom that is hard to tolerate; causes interference with activities of daily living and/or sleeping).

# 3.1.4.7 Daily 3CS Score through Week 28/Follow Up

The daily 3CS score is the sum of the daily scores of the 3 cardinal symptoms (nasal blockage/obstruction/congestion, facial pain/pressure, and anterior/posterior nasal discharge). If any of the 3 daily scores is missing, the daily 3CS score will be considered missing.

## 3.1.4.8 Weekly Individual CS Score through Week 28/Follow Up

The nasal blockage/obstruction/congestion (or anterior/posterior nasal discharge or facial pain/pressure or reduction/loss of smell) score for a week is the average of the non-missing daily scores over the 7-day period of the week. If less than 4 daily scores are available for a week, the individual CS score will be considered missing for that week.

# 3.1.4.9 Weekly 3CS Score through Week 28/Follow Up

The 3CS score for a week is the average of the non-missing daily 3CS scores over the 7-day period of the week. If less than 4 daily 3CS scores are available for a week, the 3CS score will be considered missing for that week.

# 3.1.4.10 CRS-PRO through Week 28/Follow Up

The CRS-PRO questionnaire is a 12-item disease-specific health-related impairment for use in CRS. The questionnaire assesses CRS in 3 domains including physical symptoms, sensory impairment, and psychosocial effects. Subjects will score the severity of their CRS symptoms on a 5-point scale over the past 7 days, with higher score representing worse quality of life: 0 = not at all, 1 = a little bit, 2 = somewhat, 3 = quite a bit, 4 = very much.

The scores are summed; higher scores on the CRS-PRO instrument total score or subdomain scores (as defined in Table 4) indicate higher severity of CRS symptoms.

If any of the individual item scores is missing, the total score and the corresponding domain score will be considered missing.

Table 4. Categorized Survey Items for Separate Domains of the CRS-PRO Instrument

CRS-PRO Domains	Survey Items	Score Range
Physical Symptoms	#1, #2, #3, #4, #5, #6, #7	0–28
Sensory Impairment	#8	0–4
Psychosocial Effects	#9, #10, #11, #12	0–16

#### 3.1.4.11 Rescue Treatment Recommendation through Week 28/Follow Up

Rescue treatment is defined as, after subject enrollment, worsening of or uncontrolled severe symptoms of CRS in a subject resulting in the treating physician reporting an escalation of

treatment, including SCS, and/or sinonasal surgery. Rescue treatment is not recommended if worsening of symptoms is for less than 3 days duration. The following rescue medication is recommended:

- A course of oral or systemic corticosteroids. Typical indications include persistent sinus
  infection after an initial course of antibiotics while starting another course of antibiotics,
  uncontrolled sinus inflammation, or a flare-up of asthma. The dose, duration of use, and
  rationale for the use of oral or systemic corticosteroid must be recorded.
- Sinonasal surgery as rescue treatment according to the Investigator's recommendation. The type and rationale for sinonasal surgery must be recorded.

The rescue treatment recommendation through Week 28/Follow Up is derived by checking whether the rescue treatment is taken before Week 28/Follow Up, inclusive. If a subject is lost to follow up/discontinues the study before Week 28/Follow Up and does not have rescue treatment requirement at that time, then it will be considered as missing data.

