9.8.1.2 Time-to-First Recommendation of Rescue Treatment

This efficacy endpoint is to analyze the first time a subject uses rescue treatment for worsening of CRS symptoms. Rescue treatment is defined as, after subject enrollment, worsening or acute exacerbation of CRS in a subject resulting in the treating physician reporting an escalation of

treatment with either systemic corticosteroids (SCS) and/or sinonasal surgery. Time to first recommendation of rescue treatment will be analyzed using Kaplan-Meier (K-M) method. The K-M estimate of median time to first recommendation of rescue treatment (if estimable) will be presented for each treatment group. The K-M curve of time to first recommendation of rescue treatment will be compared between each LYR-220 group and the sham procedure group using the log-rank test.

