9.8.1.3 Oral Steroids or Sinonasal Surgery Recommendation

The endpoint will be summarized using the percentage of subjects being recommend by treating physician for oral/systemic steroids (SCS) or sinonasal surgery in each treatment group. Comparison between each LYR-220 group and the sham procedure group will be performed using a Cochran-Mantel-Haenszel (CMH) test controlling for nasal polyp status.

9.8.1.4 CFBL in Bilateral Percent Ethmoid Cavity Opacification by CT at Week 25

Mean CFBL in bilateral percent ethmoid cavity opacification by CT at Week 28 will be compared between each LYR-220 group and the sham procedure group using an ANCOVA model with fixed-effect terms for treatment group and nasal polyp status with baseline score as a covariate.

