## 2.3.3 Secondary Efficacy Endpoints

The secondary efficacy endpoints are:

- 1. Change from baseline (CFBL) in SNOT-22 total and subdomain scores at Weeks 2, 4, 6, 8, 12, 16, 20, 24, and 28/Follow Up.
- 2. CFBL in the 7-day average composite score of 3CS and individual cardinal symptom scores at Weeks 2, 4, 6, 8, 12, 16, 20, 24, and 28/Follow Up.
- 3. CFBL in the 7-day average score of loss of smell for subjects with baseline score ≥2 at Weeks 2, 4, 6, 8, 12, 16, 20, 24, and 28/Follow Up.
- 4. CFBL in CRS-PRO total and subdomain scores at Weeks 2, 3, 4, 6, 8, 12, 16, 20, 24, and 28/Follow Up.
- 5. Time to first rescue treatment recommendation through Week 28/Follow Up.
- 6. Systemic/oral corticosteroid use or sinonasal surgery recommendation through Week 28/Follow Up.
- CFBL in bilateral percent ethmoid cavity opacification by CT at Week 25/Follow Up.
- 8. CFBL in PGIS score at Weeks 8, 16, and 24.
- 9. PGIC score at Week 24.
- 10. No longer a candidate for revision surgery.
- 11. CFBL in nasal inflammatory marker levels at Week 25/Follow Up.

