## 3.1.4.12 Time to First Rescue Treatment Recommendation through Week 28/Follow Up

Time to first rescue treatment recommendation will be counted from date of insertion procedure, i.e., date of first rescue treatment recommendation – date of LYR-220 administration/sham insertion procedure + 1. If a subject is lost to follow up/discontinues the study before Week 28/Follow Up and does not have rescue treatment requirement by that time, then it will be censored at the date of last assessment. If a subject does not have rescue treatment required through Week 28/Follow Up, it will be censored at Week 28/Follow Up.

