#### 3.1.4.16 No longer a candidate for revision surgery

Subjects will be deemed as having converted if they do not undergo revision sinonasal surgery (planned or actual) during the study and if they meet the following criteria:

- 3CS score ≤4 at Week 24, or
- No disease in ethmoid cavities on Week 25/Follow Up CT.

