Time to first recommendation of rescue treatment will be analyzed using Kaplan-Meier (K-M) method. The K-M estimate of median time to first recommendation of rescue treatment with CI (if estimable) will be presented for each treatment group. K-M estimates of quartiles (25th and 75th percentiles) will also be presented for each treatment group.

#### 3.4.2.5.2 Part 2

Time to first recommendation of rescue treatment will be analyzed using Kaplan-Meier (K-M) method. The K-M estimate of median time to first recommendation of rescue treatment with CI (if estimable) will be presented for each treatment group. Estimates of quartiles (25th and 75th percentiles) will also be presented for each treatment group. Time to first recommendation of rescue treatment will be compared between LYR-220 group and the sham procedure group using the log-rank test stratified by the stratification factor. P-value from the log-rank test will be presented.

K-M estimates of the survival function for time to first recommendation of rescue treatment will be graphically displayed for each treatment group.

3.4.2.6 Systemic/Oral Corticosteroid Use or Sinonasal Surgery Recommendation through Week 28/Follow-up

#### 3.4.2.6.1 Part 1

The endpoint will be summarized using the number and percentage of subjects being recommend by treating physician for systemic/oral steroid use or sinonasal surgery in each treatment group.

#### 3.4.2.6.2 Part 2

The endpoint will be summarized using the number and percentage of subjects being recommended by treating physician for systemic/oral corticosteroid use or sinonasal surgery in each treatment group. Comparison between LYR-220 group and the sham procedure group will

be performed using a Cochran-Mantel-Haenszel (CMH) test controlling for nasal polyp status. The general association p-value will be provided. The odds ratio and the corresponding Cl will also be provided. The point estimates and Cl for the treatment group differences in proportions will be calculated using Agresti's (2013, page 231) approximation to the Miettinen and Nurminen (1985) method by using pseudo-standard errors.

3.4.2.7 CFBL in Bilateral Percent Ethmoid Cavity Opacification by CT at Week 25/Follow-up 3.4.2.7.1 Part 1

Descriptive summary statistics on the values and changes from baseline to Week 25/Follow-up will be presented.

3.4.2.7.2 Part 2

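### SAP 3.1.4.11 derives the yes/no rescue-recommendation endpoint from rescue taken, while the analysis section, the protocol and the time-to-event definition count rescue recommended

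*SAP*

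**What the plan says.** SAP 3.1.4.11 is headed as a recommendation endpoint and defines rescue as worsening or uncontrolled severe CRS that leads the treating physician to report an escalation of treatment. Its derivation sentence then uses a different trigger: "The rescue treatment recommendation through Week 28/Follow Up is derived by checking whether the rescue treatment is taken before Week 28/Follow Up, inclusive". The missing-data sentence that follows uses a third term. A subject who leaves the study early and "does not have rescue treatment requirement at that time, then it will be considered as missing data".

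The other descriptions of the same event turn mainly on recommendation:

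- SAP 2.3.3, item 6, names the endpoint "Systemic/oral corticosteroid use or sinonasal surgery recommendation through Week" 28/Follow Up.
- SAP 3.4.2.6.2, which specifies the CMH test, summarises the "percentage of subjects being recommended by treating physician for systemic/oral corticosteroid use or sinonasal surgery".
- Protocol 9.8.1.3 summarises "the percentage of subjects being recommend by treating physician for oral/systemic steroids (SCS) or sinonasal surgery".
- SAP 3.1.4.12 defines the time-to-event version: "Time to first rescue treatment recommendation will be counted from date of insertion procedure, i.e., date of first rescue treatment recommendation".
- SAP 3.1.4.16 classes subjects as converted only "if they do not undergo revision sinonasal surgery (planned or actual) during the study", so there a planned operation counts.

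Protocol 9.8.1.2 is mixed. Its heading speaks of recommendation, but its first sentence reads "This efficacy endpoint is to analyze the first time a subject uses rescue treatment for worsening of CRS symptoms".

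Protocol 8.3.7 and SAP 3.6.7 provide for rescue surgery scheduled after the planned end of study. They also provide for subjects who stop treatment, complete the end-of-treatment assessments before the operation, and are then discontinued. For surgery done or scheduled, the eCRF records the date it was indicated as well as the expected or actual date.

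**The concern.** Recommendation and receipt are different events, and the plan itself expects a gap between them for surgery. A patient can fail treatment, be told that revision surgery is needed, and still not have had the operation when follow-up closes. Under the derivation rule that patient looks rescue-free; under the analysis section the same patient is a failure. Two programmers could each follow the SAP faithfully and produce different event counts. The CMH and log-rank results on what should be the same event could also differ because of wording alone.

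Timing adds to this. SAP 4.2 unblinds allocation at the Primary Lock. The rescue endpoints are not among the outputs listed for that lock, so they are first analysed afterwards. If the wording is still open then, a reading would be chosen with allocation known, and the SAP classes later changes that affect the analysis as post hoc.

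**Working it through.** The documents state no event rate, power or sample size that depends on this definition, so there is no figure to reproduce. The check is to classify the affected subjects under each rule.

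| Subject | SAP 3.1.4.11 (taken) | SAP 3.4.2.6.2 and Protocol 9.8.1.3 (recommended) | SAP 3.1.4.12 (recommendation date) |
|---|---|---|---|
| A. Completer; surgery indicated in-study, scheduled after study end; no corticosteroid rescue | Non-event | Event | Event |
| B. Discontinued for surgery not yet done when follow-up closes; no corticosteroid rescue | Not an event, and not missing | Event | Event |
| C. Corticosteroid recommended, never taken | Non-event if a completer | Event | Event |
| D. Left the study early, no rescue needed | Missing | No separate rule | Censored |

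Row B follows from reading the two sentences of 3.1.4.11 together. The subject has not taken rescue, so is not an event. The missing rule covers only early leavers without a rescue requirement, and this subject has one. By default the subject counts as rescue-free. Row D is handled consistently and needs no change.

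If the 3.1.4.11 variable is instead taken to feed 3.1.4.12, the Kaplan-Meier analysis loses subjects A to C too. The two analyses then agree with each other but not with the text of 3.4.2.6.2.

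**Effect of one subject.** SAP 2.2.1 plans 20 per arm, so one reclassified subject moves the arm rate by 1/20 = 5.0 percentage points. Since the number is approximate, I also took 18 and 22 per arm: 1/18 = 5.6 and 1/22 = 4.5 points.

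**Illustration with assumed counts.** Take a single stratum, n = 20 per arm, N = 40, a events on LYR-220, b on sham and m = a + b. The CMH statistic is (a − m/2)² / v, with v = n²·m·(N − m) / [N²·(N − 1)], on 1 degree of freedom.

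- 1 vs 6 recommended: m = 7, v = 400·7·33/62,400 = 1.481; 2.5²/1.481 = 4.22; two-sided p = 0.040.
- One sham operation pending and not counted, 1 vs 5: v = 400·6·34/62,400 = 1.308; 2²/1.308 = 3.06; p = 0.080.
- Two pending on sham, 1 vs 4: v = 400·5·35/62,400 = 1.122; 1.5²/1.122 = 2.01; p = 0.157.
- The single LYR-220 event pending instead, 0 vs 6: v = 1.308; 3²/1.308 = 6.88; p = 0.009.

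The last two lines move in opposite directions from the same start. The counts are invented; they show only that one or two subjects matter at this sample size and that the shift can go either way.

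**The case against.** The strongest reply is that *taken* is a slip in a scheme otherwise built on recommendation. The definition in 3.1.4.11 rests on the physician reporting an escalation, the variable is named a recommendation, the missing rule speaks of a requirement, and the section that specifies the CMH test counts recommendations. A careful programmer might follow 3.4.2.6.2. The detailed programming specifications (SAP 6) are a separate document and may already settle the point. This stands in part. A reader might infer that the CMH analysis will lose pending surgery; the documents support that only if 3.1.4.11 is followed over 3.4.2.6.2. But 3.1.4.11 is the derivation section and 3.4.2.6.2 gives no data rule, so the conflict remains. SAP 5 declares no change from the protocol analyses, so it does not present *taken* as a deliberate departure.

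Two further inferences are tempting. One is that only surgery is affected, because item 6 of SAP 2.3.3 speaks of corticosteroid use. SAP 3.4.2.6.2 and Protocol 9.8.1.3 count corticosteroid recommendations too. The other is that every subject who requires surgery is withdrawn, as the risk-benefit narrative in Protocol 11 suggests, which would make row B large. The operative text is narrower: Protocol 4.3 says that treatment may be discontinued, and Protocol 8.3.7 and SAP 3.6.7 tie discontinuation to an operation to be performed during the treatment period.

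It is also fair that planned surgery does not vanish from the report. It counts against conversion, and SAP 3.6.7 covers actual or planned surgery by arm.

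**Conclusion.** The contradiction is in the text and should be corrected. SAP 3.1.4.11 as written gives a wrong classification for subjects the plan itself foresees, and it can make the CMH and Kaplan-Meier event counts disagree. That consequence is conditional on 3.1.4.11 being programmed literally while 3.1.4.12 keeps the recommendation date.

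The size is about 5 points on an arm's rate per affected subject at 20 per arm. How many subjects would be affected is unknown, because the documents give no rescue or surgery rates. A reader might infer that the rule favours LYR-220 by hiding sham failures; nothing in the documents fixes the direction. The reach is limited to this endpoint, one of eleven secondary efficacy endpoints, with no power basis (SAP 2.2.5) and no multiplicity adjustment (SAP 3.1.7). The primary safety endpoint is unaffected.

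**What to change.** Before the Primary Lock, replace *taken* in SAP 3.1.4.11 with *recommended or indicated on or before Week 28/Follow Up*, and then:

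- Date surgery by the eCRF date on which it was indicated. SAP 3.6.7 describes that date for surgery done or scheduled, so also say how a recommendation that was never scheduled is dated.
- Date corticosteroid rescue by its recorded recommendation or, where that is not collected, by its start date. SAP 3.6.6 describes dosing dates and indication only.
- Use this single event definition for both the CMH and the Kaplan-Meier/log-rank analyses.
- Count surgery required but not yet done as an event, including in subjects who discontinue for it.
- Leave unchanged the intercurrent-event rule in SAP 3.4.2.1.1, which concerns data collected after rescue, and the missing and censoring rules for subjects without rescue.

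The cost is SAP wording and one derivation. The surgery indication date and the corticosteroid dates are already collected, the Kaplan-Meier analysis is already planned, and patient care does not change.

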#### 2.2 Study Design

#### 2.2.1 Overview

This multicenter study will be conducted in a patient-blinded, two-part, randomized, parallel-group manner in approximately 50 symptomatic adult subjects with CRS who have had a prior bilateral ethmoidectomy. The safety, tolerability, pharmacokinetics, and efficacy of 2 designs, LYR-220-32 drug matrix and LYR-220-16 drug matrix, will be assessed in Part 1. Both designs of LYR-220 matrices contain 7500 µg of mometasone furoate (MF).

[figure not shown]
The study will consist of 2 parts. In Part 1 of the study, up to 10 subjects will be treated with either design of LYR-220 bilaterally. The primary objective of the Part 1 study, in addition to the safety and pharmacokinetics assessments of LYR-220, is to evaluate the feasibility of placement and optimize the LYR-220 insertion procedure before beginning Part 2 of the study, in which approximately 40 subjects (20 per treatment arm) will be randomized 1:1 to either LYR-220-32 (7500  $\mu$ g) or a sham procedure.

Each subject will undergo 3 stages during the study:

- Screening and Run-in Stage: 2-4 weeks
- Treatment Stage: 24 weeks
- Post-treatment Follow-Up Stage: 4 weeks

The overall study design flow diagram of subject enrollment and follow-up schedule is shown below.

Figure 1: Study Design Schematic

The schedule of study assessments for subjects is summarized in protocol Section 8.1. All subjects in Part 1 and Part 2 will undergo these study assessments per the schedule.

Vital signs and a limited physical exam, focusing on physical appearance of head, eyes, ears, nose, and throat (HEENT) will be performed at Screening visit. Samples for hematology and chemistry will be collected at Screening and Week 25/Follow Up visits.

Nasal cavities will be assessed by endoscopy at Screening, Day 1 (before the LYR-220 insertion procedure), and at Weeks 4, 12, 24 (before LYR-220 removal), and Week 25/Follow Up visits. Local safety evaluation of the ethmoid cavity will be performed at these visits to document presence of epistaxis, mucosal injury, and any other local adverse effects. On Day 1 (before LYR-220 insertion) and at Week 25/Follow Up visits, nasal swabs will be collected in ethmoid cavities to evaluate the impact of LYR-220 on nasal inflammatory marker level by protein and mRNA assays.

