#### 2.2.5 Sample Size Determination

Because the primary objective of this study is to assess the safety, tolerability, and pharmacokinetics of LYR-220, the sample size determination is not based on statistical power considerations. Up to 10 subjects will be treated in the Part 1 and approximately 40 subjects will be treated in Part 2 of the study, respectively.

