3.1.10.2 Algorithm for Treatment Emergent Adverse Events (TEAE)

TEAE is defined in Section 3.6.1.

For deriving the TEAE flag, the following process of temporary date imputation is done for adverse event (AE) start date. The date imputation algorithm for incomplete adverse event start dates is described in the following table. Classification of adverse event (TEAE or not) is then done using the imputed date.

In the following table, all dates are presented using an YYYY-MM-DD format. As an example, suppose the investigational medicinal product (IMP) administration = 2022-08-11 and several AEs have incomplete start dates.

Table 6. Imputation Rules for Missing AE start Date

Description of incomplete date   Imputed nume		Example	
	date	Character date	Imputed date
Day is missing			
YYYY-MM < YYYY-MM of [IMP	YYYY-MM-01	2022-07-XX	2022-07-01
admin.]			

YYYY-MM = YYYY-MM of [IMP	Min ([IMP admin.],	2022-08-XX	Min (2022-08-
admin.]	AE end date)		11, AE end date)
YYYY-MM > YYYY-MM of [IMP	YYYY-MM-01	2022-09-XX	2022-09-01
admin.]			
Day and month are missing			
YYYY < YYYY OF [IMP admin.]	YYYY-01-01	2021-XX-XX	2021-01-01
YYYY = YYYY OF [IMP admin.]	Min ([IMP admin.],	2022-XX-XX	Min (2022-08-
	AE end date)		11, AE end date)
YYYY > YYYY OF [IMP admin.]	YYYY-01-01	2023-XX-XX	2023-01-01
Day, month, and year are missing			
XXXX-XX-XX	Min ([IMP admin.],		Min (2022-08-
	AE end date)		11, AE end date)

YYYY = non-missing year, MM = non-missing month, DD = non-missing day, XX = missing field.

Actual data values as they appear in the original eCRFs will be presented in the data listings.

3.1.10.3 Handling of Missing Data and Data Post-Rescue Treatment for Efficacy Endpoints 3.1.10.3.1 Part 1

No imputation will be performed. All efficacy data will be summarized descriptively.

#### 3.1.10.3.2 Part 2

The details for handling missing data and intercurrent events for the secondary efficacy endpoints are specified in the estimand framework in Section 3.4.2. There will be no imputation for missing bilateral percent ethmoid cavity opacification by CT or nasal inflammatory biomarker assessments.

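### SAP 3.1.4.11 keeps rescued early leavers as events but sets rescue-free early leavers to missing, which tends to overstate the 28-week rescue percentage if drop-out is non-informative and can distort the CMH comparison if drop-out differs by arm

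*SAP*

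**What the plan says.** The binary rescue endpoint is "derived by checking whether the rescue treatment is taken before Week 28/Follow Up, inclusive" (SAP 3.1.4.11). A subject rescued before leaving is therefore an event. In the same section, a subject who leaves before Week 28/Follow Up and "does not have rescue treatment requirement at that time, then it will be considered as missing data".

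For Part 2, SAP 3.4.2.6.2 states: "The endpoint will be summarized using the number and percentage of subjects being recommended by treating physician for systemic/oral corticosteroid use or sinonasal surgery". The comparison with sham will "be performed using a Cochran-Mantel-Haenszel (CMH) test controlling for nasal polyp status. The general association p-value will be provided", together with an odds ratio and a difference in proportions. The section gives no imputation, denominator or sensitivity analysis. SAP 3.1.10.3.2 says that the details for "handling missing data and intercurrent events for the secondary efficacy endpoints are specified in the estimand framework in Section 3.4.2", but Section 3.4.2 has no rule for this endpoint. SAP 3.1.5 promises that denominators will be defined, and for this percentage none is.

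The time-to-rescue endpoint treats the same leavers differently. If a subject leaves without rescue, "then it will be censored at the date of last assessment" (SAP 3.1.4.12). SAP 3.4.2.5.2 then plans Kaplan-Meier curves, median, quartiles and a stratified log-rank test, but no Week 28 estimate.

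On size, "approximately 40 subjects (20 per treatment arm) will be randomized 1:1 to either" LYR-220-32 or sham (SAP 2.2.1), and "the sample size determination is not based on statistical power considerations" (SAP 2.2.5).

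**The concern.** Whether an early leaver is classified depends on the outcome. Those rescued first are retained, and those still rescue-free are set aside with all the rescue-free time they contributed. Keeping rescued leavers as events is correct; the fault lies in discarding the others' follow-up. Both kinds of leaver are to be expected, because rescue surgery during the treatment period itself takes the subject out of the study (Protocol 8.3.7, SAP 3.6.7).

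At stake are the reported rescue percentage in each arm and, if drop-out differs by arm, the CMH result. Unequal drop-out is plausible: loss of both matrices triggers an early-termination visit (Protocol 4.1.2), and sham subjects have no matrix to lose. The binary and time-to-event results could then disagree on the same data, and the SAP does not say how to read them.

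**Working it through.** **Inputs.** About 20 subjects per arm in Part 2 (SAP 2.2.1). Rescued leavers are events and rescue-free leavers are missing (SAP 3.1.4.11). The documents state no rescue risk, drop-out rate or power, so there is no planned figure to reproduce. Assumed ranges: true 28-week rescue risk p of 10–40%, and drop-out d by Week 28 of 5–30%.

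**Step 1: non-informative drop-out.** Take constant, independent hazards over 28 weeks:

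- rescue hazard λ = −ln(1−p)/28; drop-out hazard γ = −ln(1−d)/28
- rescued before leaving: E = λ/(λ+γ) × [1 − exp(−28(λ+γ))]
- rescue-free completers: C = exp(−28(λ+γ)) = (1−p)(1−d)
- percentage under the rule, with missing subjects excluded: E/(E+C)

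For p = 30% and d = 30%, the hazards are equal, C = 0.7 × 0.7 = 0.49 and E = 0.5 × 0.51 = 0.255. The rule gives 0.255/0.745 = 34.2%. For p = 30% and d = 5%, C = 0.665, E = 0.293 and the rule gives 30.6%.

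Bias in percentage points:

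| True risk p | d = 5% | d = 10% | d = 20% | d = 30% |
|---|---|---|---|---|
| 10% | +0.2 | +0.5 | +1.1 | +1.8 |
| 20% | +0.4 | +0.9 | +2.0 | +3.2 |
| 30% | +0.6 | +1.2 | +2.6 | +4.2 |
| 40% | +0.7 | +1.4 | +3.0 | +4.8 |

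**Step 2: comparison of arms.** With an equal true risk of 30% and drop-out of 30% against 5%, the rule shows 34.2% against 30.6%, a false gap of about 3.7 points before rounding. In 20,000 simulated trials of 20 per arm (polyp strata of 14 and 6 per arm, assumed), the CMH statistic at one-sided 0.05 rejected 8.2% of the time against the high-drop-out arm and 3.1% in its favour. The two-sided error was 5.5%. With equal risk and equal drop-out of 15%, the one-sided errors were 5.2% and 5.0%.

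With unequal risks the gap can move either way. For a true difference of −20 points (10% against 30%), the rule shows −18.8 points when drop-out is 30% against 5%, and −23.1 points when it is 5% against 25%.

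**Step 3: informative drop-out.** Let N be the arm size, E the number rescued, M the number of rescue-free leavers and q their later rescue risk. The rule gives E/(N−M) and the truth is (E+qM)/N, so the rule overstates only if q < E/(N−M). For N = 20, E = 4 and M = 3, the rule gives 4/17 = 23.5%. The truth lies between 4/20 = 20% and 7/20 = 35%. At q = 50% it is 5.5/20 = 27.5%, and the rule is too low.

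**Step 4: alternatives.** Counting every subject in the denominator, with leavers as not rescued, gives the proportion E. That is 25.5% for a true 30% at 30% drop-out, and 18.0% for a true 20% at 20% drop-out. In the scenario of Step 2 it gives 25.5% against 29.3%, a false gap of 3.8 points in the opposite direction. Kaplan-Meier with the censoring of SAP 3.1.4.12 targets p itself under non-informative drop-out.

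**The case against.** The strongest reply is that a sound analysis of these events is already planned. The time-to-event endpoint censors leavers and applies a stratified log-rank test. That stands, and it limits the damage, but it leaves the percentage, odds ratio and risk difference uncorrected, and no Week 28 Kaplan-Meier figure is planned to set beside them.

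The exclusion of missing subjects is also inferred. SAP 3.4.2.6.2 does not refer back to 3.1.4.11, and SAP 3.4 bases efficacy summaries on the Efficacy Analysis Set. Under an all-subject denominator the error would be downward. The point stands in either case, since neither denominator gives the 28-week risk.

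The size is modest. Drop-out of 5% against 30% means 1 against 6 leavers out of 20. The resulting false gap is smaller than one subject (5 points) and well below the standard error of the difference, √(2 × 0.3 × 0.7/20) = 14.5 points. Subjects rescued with systemic corticosteroids stay in the study (SAP 3.6.6), and those with an early-termination visit are asked to stay for the Week 25 assessments (Protocol 4.1.2), so early leaving may be limited. The endpoint is secondary and unpowered. All of this bears on priority and does not justify the rule.

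A reader might infer more: that the percentage and the CMH comparison are always biased upward, and most in the arm with more drop-out. The documents do not support this. The upward direction needs non-informative drop-out (Step 3). With equal risk, the CMH test is distorted only when drop-out differs (Step 2). The bias also grows with risk: a 10% risk with 20% drop-out gives +1.1 points, while a 40% risk with 15% drop-out gives +2.2, so the larger error can sit in the arm with less drop-out.

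**Conclusion.** The concern holds in conditional form. The asymmetric rule is in the SAP and no other section corrects it for the percentage and the CMH analysis. If missing subjects are excluded and drop-out is non-informative, the rescue percentage is too high by about 0.2 to 5 points over the assumed ranges. If drop-out differs by arm, the p-value, odds ratio and risk difference can be distorted; the extreme case examined moved the one-sided CMH error from about 5% to 8.2% in one direction and 3.1% in the other. If leavers have a high later rescue risk, the percentage can be too low. The figures rest on constant, independent hazards and on assumed rescue and drop-out rates. For an unpowered secondary endpoint this is worth correcting, but it does not threaten the trial's main conclusions.

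**What to change.** - In SAP 3.1.4.11, replace the rule that sets rescue-free leavers to missing. As the estimate of the rescue proportion, report per arm 1 minus the Kaplan-Meier estimate at Week 28, with the time origin and censoring of 3.1.4.12. Give the between-arm difference and a 90% CI from Greenwood standard errors, stratified by polyp status where the strata allow.
- Fix the Week 28 evaluation point in days from insertion. SAP 3.1.2 anchors follow-up visits to end of treatment, so a subject who stops treatment early could otherwise pass as rescue-free through Week 28 with much less time observed.
- Keep the CMH test that Protocol 9.8.1.3 specifies and state its denominator in SAP 3.4.2.6.2. Beside it, show bounds with rescue-free leavers counted as all rescued and as none rescued, including the two opposite assignments across arms. Do not present the all-subject denominator as unbiased.

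The cost is one added estimate from curves already planned, one sensitivity table and SAP text. SAP Section 5, which now declares no changes from the protocol-specified analyses, must list the addition. No new data are needed. Under informative drop-out Kaplan-Meier is also biased, which is why the bounds are needed.
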